9 STUDY ADMINISTRATION, DATA HANDLING AND RECORD KEEPING	9
9.1 CONFIDENTIALITY.....	9
9.2 DATA COLLECTION AND MANAGEMENT	9
10 STUDY MONITORING, AUDITING, AND INSPECTING	9
10.1 STUDY MONITORING PLAN.....	9
10.2 AUDITING AND INSPECTING	10
11 ETHICAL CONSIDERATIONS	10
11.1 RISKS.....	10
11.2 BENEFITS	10
11.3 RISK BENEFIT ASSESSMENT	11
11.4 INFORMED CONSENT PROCESS / HIPAA AUTHORIZATION	11
12 STUDY FINANCES	11
12.1 FUNDING SOURCE.....	11
12.2 CONFLICT OF INTEREST	11
12.3 SUBJECT PAYMENTS	11
13 BENCHMARKS FOR STUDY/PUBLICATION PLAN	11

CONFIDENTIAL

List of Abbreviations

CDT: Complete decongestive therapy

HNC: Head and neck cancer

LLLT: Low-level laser therapy

Study Summary

Title	Low-Level Laser in Treatment of Head and Neck Lymphedema: A Pilot Study
Short Title	Low-level laser therapy in head and neck lymphedema
Study ID Number	UPCC12318
Protocol Number	Version Date: 06-15-2019
Phase	Pilot study
Methodology	A single-arm, pre- and post-design clinical trial
Study Duration	24 months
Study Center(s)	Single-center
Objectives	
Primary aim: To determine the feasibility of the use of LLLT for HNC survivors with lymphedema, specifically to 1) obtain recruitment estimates and determine barriers to recruitment; 2) identify barriers to implementation; 3) assess safety; and 4) evaluate patient satisfaction.
 
Secondary aim: To determine the preliminary efficacy of the use of LLLT on the following outcomes: 1) lymphedema progression; 2) symptom burden; and 3) functional status.

Number of Subjects	25 subjects expected to be enrolled
Main Inclusion and Exclusion Criteria	
Inclusion criteria: >18 years of age; 2) completion of either postoperative radiation or chemoradiation therapy; 3) no evidence of cancer; 4) having head and neck external lymphedema; 5) ability to speak and read English; and 6) able to provide informed consent.
 
Patients will be excluded if they have any of the following medical conditions that would prohibit the safe implementation of LLLT: pregnancy; photosensitivity; chronic inflammatory diseases; venous thrombosis; history of severe trauma; medication that affects body fluid and electrolyte balance; use of high doses of non-steroidal anti-inflammatory drugs; or pre-existing skin rash, ulceration, open wound in the treatment area; and allergic and other systemic skin diseases.

Investigational device For Device include the planned use	RianCorp LTU-904 Low-level laser therapy unit
Duration of administration (if applicable)	6 weeks
Safety Evaluations	Common Terminology Criteria for Adverse Events (CTCAE version 4.03) will be used to document adverse events of the clinical trial
Data and Safety Monitoring Plan	PI [name] will be responsible for monitoring the data quality and the ongoing safety of subjects.

BACKGROUND AND STUDY RATIONALE

This study will be conducted in full accordance all applicable University of Pennsylvania Research Policies and Procedures and all applicable Federal and state laws and regulations including the use of a medical device (i.e., RianCorp LTU-904).

1 Introduction

Current standard of care for head and neck lymphedema treatment provided by therapists is short-term in nature (usually up to 4-12 weeks); however, lymphedema is a chronic condition and often worsens over time. Therefore, alternative treatment modalities need to be investigated for effective and long-term management of lymphedema and associated late fibrosis in the head and neck cancer (HNC) population.

1.1 Background and Relevant Literature

There has been an increase in the incidence of head and neck cancer (HNC) largely related to the epidemic of human papillomavirus (HPV) associated disease.^{1,2} HPV- associated HNC occurs in younger and middle-aged patients; cure rates in this population are markedly higher compared to other HNC groups.^{3,4} This contributes to more than half a million HNC survivors in the U.S. today.⁵ Regardless of cause, patients with locally advanced HNC are usually treated with aggressive multi-modality regimens.⁶ These regimens often lead to numerous long-term toxicities. One common but under-treated late effect of treatment is damage to lymphatic structures and soft tissues resulting in lymphedema.^{7,8} Animal studies indicate that lymphedema is associated with chronic inflammation leading to fibrosis.^{9,10} Our work was the first to assess lymphedema in HNC patients in a systematic manner.^{7,11} We demonstrated a prevalence rate of 75% in HNC survivors.⁷ We confirmed that lymphedema occurs both externally (e.g., face and neck) and internally (e.g., pharynx and larynx).^{7,12} Subsequent work demonstrated that external lymphedema resulted in a decreased range of motion in the jaw, neck and shoulders.¹³ Internal swelling was found to cause substantial impact on critical functions (e.g., swallowing, speaking, and breathing).^{13,14} Psychological effects (e.g., body image disturbance) were also correlated with lymphedema.^{13,15-17} Finally, lymphedema has the potential to negatively impact HNC survivors' ability to function in both home and work environments, resulting in both emotional and financial burden for these individuals, their families, and the healthcare system.^{11,18}

Current standard of care for treatment of lymphedema is complete decongestive therapy (CDT), which consists of 4 main parts: manual lymphatic drainage, compression (bandaging or garments), exercise, and skin care.^{10,19,21,22} These treatments are expensive, time-consuming and labor-intensive. CDT provided by therapists is short-term in nature (usually up to 4-12 weeks); however, lymphedema is a chronic condition and often worsens over time.^{10,19} Therefore, alternative treatment modalities need to be investigated for effective and long-term management of lymphedema and associated late fibrosis in the HNC population.

Among many alternative treatment options, low level laser therapy (LLLT) is a promising, noninvasive modality for treatment of lymphedema. LLLT, also named photobiomodulation therapy (PBMT), has had a place in general medicine for more than 40 years.²⁴ It has been used as a treatment option to stimulate wound healing and reduce inflammation, edema, and pain.²⁴ The U.S. Food and Drug Administration (FDA) accepted it as a treatment approach for breast cancer-related upper extremity lymphedema (BCRL) in 2006.²⁴ One recent systematic review evaluating 7 randomized clinical trials (RCT) concluded that available evidence supports LLLT in the management of BCRL, with clinically meaningful reductions in lymphedema-related swelling and symptom burden (e.g., pain).²⁵ Compared to other treatment modalities, LLLT is a noninvasive modality, repeatable, easily performed in outpatient setting, and without any known long-term side effects. To our knowledge, the current proposal is the first study investigating the use of LLLT in the treatment of head and neck lymphedema. The goal of this proposed research is to determine the feasibility and preliminary efficacy of the use of LLLT on facial/neck swelling and fibrotic changes, symptom burden, and neck mobility in HNC survivors with lymphedema through a pilot study.

CONFIDENTIAL

1.2 Name and Description of the Investigational Product

We will use a RianCorp LTU-904, FDA-approved, Class I laser device in this study. The device will be used by the study lymphedema therapist, [name], who has had more than 20 years of experience treating individuals with lymphedema.

1.2.1 Nonclinical Data

Findings from nonclinical data indicate that LLLT stimulates lymphatic vessels and lymphocytes, as well as increases local fluid circulation.^{27,28}

1.2.2 Clinical Data to Date

Currently, only cases studies indicate the potential value of use of LLLT for treating head and neck lymphedema.^{29,30} No large prospective clinical trials are available to evaluate prophylactic and/or therapeutic use of LLLT for lymphedema in HNC patients. However, a large body of evidence is available in supporting the safety and efficacy of LLLT for management of lymphedema in breast cancer patients. For instance, since 1995, the use of LLLT has been investigated in the treatment of breast cancer-related lymphedema (BCRL).³¹ A meta-analysis of 9 studies (7 of them were RCTs) provided evidence that LLLT alone or combined with other treatments was able to reduce the arm swelling and pain in women with BCRL.³¹ LLLT does not increase the risk on cellulitis, a known side effect in patients with arm lymphedema.³¹ A recent systematic review also suggested the use of LLLT for treating the following conditions in the breast cancer population: oral mucositis, radiodermatitis, chemotherapy-induced peripheral neuropathy, and osteonecrosis of the jaw.²⁴ In another recent systematic review, the authors concluded that LLLT may have potential applications in the management of a broad range of side effects (e.g., lymphedema/fibrosis) of chemo-radiation therapy in patients with HNC.^{32, 33}

1.2.3 Clinical Studies in Children

Not applicable

1.3 Dose Rationale (if applicable)

We propose that participants will receive LLLT twice a week for 6 weeks (12 sessions). This regimen was developed based on the evidence from literature.

2 Study Objectives

The goal of this proposed research is to evaluate the effect of LLLT on facial/neck swelling and fibrotic changes, symptom burden, and neck mobility in HNC survivors with lymphedema through a pilot study.

2.1 Primary Objective

- To determine the feasibility of the use of LLLT for HNC survivors with lymphedema.

2.2 Secondary Objective

- To determine the preliminary efficacy of the use of LLLT for HNC survivors with lymphedema.

3 Investigational Plan

3.1 General Design

We will conduct a single-arm, pre-and post-design clinical trial. Outcome measures include: 1) feasibility (barriers to implementation, safety, and satisfaction) of the proposed intervention [Primary aim]; and 2) preliminary efficacy (lymphedema progression, symptom burden, and functional status) of the proposed intervention [Secondary aim]. Study assessments will take place at baseline, immediately after end of the intervention, and 4-week post-intervention.

CONFIDENTIAL

3.1.1 Screening Phase

We will recruit a minimum of 6 participants per month. The volume of HNC patients at Penn's Clinic is sufficient to complete this trial without additional sites. The following recruitment procedures will be used: screening at HNC clinics and attendance at Head and Neck tumor board and case conferences. All direct patient recruitment activities will be conducted at the Penn HNC clinics where private rooms are available to be used for conducting clinical research projects.

3.1.2 Study Intervention Phase and Follow Up Phase

After completion of the baseline measures, participants will be scheduled for LLLT. The LLLT includes receiving LLLT twice a week for 6 weeks (12 sessions) (LLL protocol developed based on the literature review³⁴⁻⁴¹). After completion of the 12-session LLLT, participants will be given a) contact information and instructions to call for problems and b) a calendar outlining dates for 4-week follow-up data collection.

3.2 Study Endpoints

3.2.1 Primary Study Endpoints

The primary endpoint will be the feasibility of LLLT in HNC patients, including recruitment estimates, barriers to recruitment, and barriers to implementation, safety, as well as patient satisfaction.

3.2.2 Secondary Study Endpoints

The secondary study endpoint will be the potential efficacy of LLLT in HNC patients, including lymphedema progression, symptom burden, and functional status.

4 Study Population and Duration of Participation

4.1 Inclusion Criteria

- >18 years of age
- Completion of either postoperative radiation or chemoradiation therapy
- No evidence of cancer
- Having head and neck external lymphedema
- Ability to speak and read English
- Able to provide informed consent

4.2 Exclusion Criteria

Patients will be excluded if they have any of the following medical conditions that would prohibit the safe implementation of LLLT: pregnancy; photosensitivity; chronic inflammatory diseases; venous thrombosis; history of severe trauma; medication that affects body fluid and electrolyte balance; use of high doses of non-steroidal anti-inflammatory drugs; or pre-existing skin rash, ulceration, open wound in the treatment area; and allergic and other systemic skin diseases. In addition, patients will be excluded if they are in active physical therapy and/or lymphedema therapy.

4.3 Subject Recruitment

The following recruitment procedures will be used: screening at HNC clinics and attendance at Head and Neck tumor board and case conferences. All direct patient recruitment activities will be conducted at the Penn HNC clinics where private rooms are available to be used for conducting clinical research projects.

4.4 Duration of Study Participation

The duration of the study subjects' participation will be 10 weeks, including screening, study intervention phase (6 weeks) and follow up time period (up to 4 weeks).

CONFIDENTIAL

4.5 Total Number of Subjects and Sites

Total number of subjects: 25

Single-site study: Subjects will be enrolled at Penn only.

4.6 Vulnerable Populations

Not applicable.

5 Study Intervention (Study drug, device, biologic, vaccine, food etc.)

5.1 Description

The LTU-904 is a Class I laser device, which is a low output laser in the infrared wavelength (904nm) and no safety glasses are required as there is no risk of eye damage as defined by the standards set by the international Electrotechnical Commission.

5.2 Intervention Regimen

The LTU-904 will be used in the study. The following laser parameters commonly used in the literature will be used in the study: 5mW output; 904nm wavelength in pulsed mode; dosage (energy density) of 1.5J/cm². For this pilot study, all the study participants will receive the same treatment regimen, including the same dose, therapy sessions, and treatment spots.

Participants will undergo the following procedures at each study visit. First, they will be asked to lie on a massage table. Then, the study lymphedema therapist will place a small laser device head directly on the skin of either left side or right side of the participant's face and neck, i.e., the side with the swelling and the tough/tight tissues. A total of 14 ~25 spots on the face and neck will be treated. The spots includes: maxillary prominence (1 spot), mandible (2 points), pre auricular (1 point), submental (3 points), sternocleidomastoid muscle (3 points), supraclavicular area (2 points), and scalene muscle (2 points). Each spot will be treated for about 60 seconds. Each study visit will take approximately 25-30 minutes. Prior to low-level laser therapy, participants will receive 5 minutes of simple manual lymphatic drainage (MLD) to the head and neck region that followed the international standards.

5.3 Storage

Study Device Storage, Delivery and Management: The LTU-904 will be purchased from RianCorp directly. The device will be shipped to the PI directly. The LTU-904 unit comes with a carry case that ensures the unit is stored safely. Both the PI [name] and the study lymphedema therapist ([name]) will be trained by an expert from RianCorp directly regarding how to store, dispense, and manage the device appropriately prior to subject enrollment or conducting research activity. The study lymphedema therapist will be responsible for storing, dispensing, and managing the laser device. The study lymphedema therapist will evaluate and monitor the LTU-904 unit regularly to ensure its normal function and prepare it for administration to subjects. The study lymphedema therapist will make sure the LTU-904 is stored properly after use of the device each time. The study lymphedema therapist will report the failed device to the PI [name]. The PI [name] will return the failed device to the manufacturer. The PI [name] will monitor the storage, delivery, and management of the laser device throughout the study.

5.4 Preparation and Packaging

The study lymphedema therapist ([name]) will properly prepare the LTU-904 unit for administration to subjects. [name] will make sure the LTU-904 is stored properly after use of the device each time.

5.5 Blinding

Not applicable.

CONFIDENTIAL

5.6 Subject Compliance Monitoring

The participants are encouraged to be compliant with the scheduled visits. The reasons for non-compliance with the study scheduled visits will be documented and potential underlying barriers will be explored.

6 Study Procedures and Data Collection

6.1 Screening

The screening will be conducted by a trained staff member. Individuals who are interested in this research will be screened for eligibility for being in the study. A Screening Checklist will be used to ensure that eligible participants are enrolled in the study. A Recruitment Log will be used during the recruitment.

6.2 Study Intervention Phase

6.2.1 Visit 1: Baseline Visit

The following procedures and data collection will take place at study visit 1.

- Demographic Form
- Physical Exam for completing HN-LEF Grading Criteria
- Digital photographs of face and neck
- Modified Patterson Scale
- Symptom burden assessments (LSIDS-H&N and NDI)
- Functional status (neck range of motion)

In addition, the following variables will be abstracted from the medical chart with participants' permission.

- HNC Disease and treatment information (HNC Clinical Form)
- Lymphedema and fibrosis diagnosis and treatment information (LEF Treatment Form)

6.2.2 Visit 2: End of Intervention

The following procedures and data collection will take place at study visit 2.

- Physical Exam for completing HN-LEF Grading Criteria
- Digital photographs of face and neck
- Modified Patterson Scale
- Symptom burden assessments (LSIDS-H&N and NDI)
- Functional status (neck range of motion)

6.2.3 Visit 3: 4 – Week post Intervention

The following procedures and data collection will take place at study visit 3.

- Physical Exam for completing HN-LEF Grading Criteria
- Digital photographs of face and neck
- Modified Patterson Scale
- Symptom burden assessments (LSIDS-H&N and NDI)
- Functional status (neck range of motion)

6.3 Subject Withdrawal

Subjects may withdraw from the study at any time without impact to their care. They may be discontinued from the study at the discretion of PI [name], due to lost follow-up or adverse events. Subjects may also be withdrawn by PI [name] from the study given safety consideration.

CONFIDENTIAL

7 Statistical Plan and Statistical Analysis

While this study is a preliminary study of efficacy and effect sizes, a maximum alpha level of 0.05 will be used for the statistical tests.

Statistical analysis for primary aim (feasibility of the intervention): Descriptive statistical and graphical methods will summarize the rates of participation (recruited vs. consented), log data (e.g., sessions completed), completion of assessments throughout the study, adverse events (safety) and satisfaction data within both groups. It is expected that $\geq 80\%$ of participants will complete the study activities, and $\geq 80\%$ will report acceptable levels of satisfaction with the interventions, thereby demonstrating feasibility of the interventions proposed in this research.

For the secondary objective, change from baseline value will be computed for each outcome variable at each follow-up timepoint. The analysis of changes over time relies on mixed-effects modeling, which accounts for correlation among subjects' repeated measures using a compound symmetry covariance matrix. Results will be reported as model-based mean change \pm standard error.

8 Safety and Adverse Events

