11.4 Informed Consent Process / HIPAA Authorization

Once the study is approved by the Penn IRB and the ACC, the trained study team members will meet with potential participants who express interest in the study. Potential study participants will be provided one copy of the informed consent to read and review. Study team members will review the study procedures and activities with potential participants. The informed consent document will be written in lay language and cover all study activities participants will engage in during the study, define the length of time the study will be conducted, and provide instructions for participant withdrawal from the study should they choose to do so. Study staff will review and, when necessary, read the informed consent document to potential participants. Participants will be given ample time and opportunity to ask questions, and all questions will be answered by study staff. The consent process will take place in a private location, with a closed door. Once participants have had an opportunity to ask questions, those questions have been answered, and they indicate an interest in participation, they will be asked to sign a written informed consent document as the study staff witnesses. In addition, the participant will be given a copy of informed consent signed by both the participant and study staff. We will not seek waivers of the informed consent process.

12 Study Finances

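### Section 7's participation rate uses undefined terms, and its feasibility verdict ignores recruitment, so feasibility could be declared with accrual far below the plan's own minimum of 6 per month.

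*Combined protocol and SAP*

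**What the plan says.** The Study Summary lists as the first part of the primary aim to "obtain recruitment estimates and determine barriers to recruitment". Section 3.2.1 repeats this in the primary endpoint, feasibility, "including recruitment estimates, barriers to recruitment, and barriers to implementation, safety, as well as patient satisfaction". Section 3.1, in contrast, leaves recruitment out of its bracketed list of feasibility outcomes.

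For analysis, Section 7 promises descriptive summaries of "rates of participation (recruited vs. consented"), together with log data (sessions completed is the example given), completion of assessments, adverse events and satisfaction. It then expects at least 80% of participants to complete the study and at least 80% to be acceptably satisfied, and says that this demonstrates feasibility. It gives no criterion for recruitment.

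Elsewhere the plan sets an accrual goal in Section 3.1.1: "We will recruit a minimum of 6 participants per month". Section 6.1 says "A Recruitment Log will be used during the recruitment", without describing its content. Section 13 names meeting recruitment goals and finishing data collection on schedule as the key benchmark, and says that the results will inform the design of a large trial.

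**The concern.** There are two linked gaps.

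The first is that the participation rate has no fixed numerator or denominator. The same study could report very different figures under the same label, depending on what the analyst takes recruited to mean. On one of the two natural readings, patients who were asked and refused never enter the calculation. Section 7 also specifies no analysis of barriers to recruitment. Section 5.6 provides for reasons for missed visits only.

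The second is that the feasibility verdict does not depend on recruitment at all. Both criteria are proportions among people already in the study, so they do not respond to how slowly those people were found or to how many declined.

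At stake is what the pilot can conclude. A larger trial needs to know how many patients must be approached for each one enrolled, and how fast enrolment runs. The plan makes these a primary question but commits to no statistic that answers the first, and it leaves the second out of its verdict.

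**Working it through.** The documents give no value, formula or target for the participation rate, so there is no stated figure to reproduce. The check compares the possible readings and then tests the verdict rule.

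**What recruited means.** Section 3.1.1 speaks of recruiting participants at a monthly rate, which implies enrolled. Section 4.3 points the other way: "All direct patient recruitment activities will be conducted at the Penn HNC clinics" describes contact with patients before consent. The text does not settle it.

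**Reading A: enrolled / consented.** Take 25 enrolled (Section 4.5). The consented counts are assumptions, and the intervals are exact (Clopper-Pearson).

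| Consented | Rate | 95% CI |
|---|---|---|
| 25 | 100% | 86.3% to 100% |
| 28 | 89.3% | 71.8% to 97.7% |
| 30 | 83.3% | 65.3% to 94.4% |
| 35 | 71.4% | 53.7% to 85.4% |

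The rate drops below 100% only through losses after consent. Refusals do not affect it.

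**Reading B: consented / approached.** Take 25 consenting. The approached counts are assumptions.

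| Approached | Rate | 95% CI |
|---|---|---|
| 28 | 89.3% | 71.8% to 97.7% |
| 36 | 69.4% | 51.9% to 83.7% |
| 50 | 50.0% | 35.5% to 64.5% |
| 84 | 29.8% | 20.3% to 40.7% |

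Every row of the second table is compatible with 25/25 = 100% in the first.

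**What both readings leave out.** Neither gives eligible/screened or approached/eligible. Section 6.1 says "Individuals who are interested in this research will be screened for eligibility for being in the study", and Section 11.4 says "the trained study team members will meet with potential participants who express interest in the study". Patients who decline before showing interest could therefore escape the count even on Reading B, unless approached is defined to include them.

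**The verdict rule.**
- Completion and satisfaction thresholds with 25 participants: 0.80 × 25 = 20 on each.
- Time to enrol 25 at the stated minimum: 25/6 = 4.2 months.
- Study duration is 24 months (Study Summary) and participation is 10 weeks (Section 4.4), or about 2.3 months. This leaves 24 − 2.3 = 21.7 months for enrolment if no start-up or analysis time falls within the 24 months.
- Slowest accrual that still fits: 25/21.7 = about 1.2 per month, and 1.2/6 = 0.2, or one fifth of the minimum.

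A study accruing at that pace, with 20 of 25 completing and 20 of 25 satisfied, meets everything that Section 7 asks for.

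**The case against.** A reader might infer that the ratio is close to 100% by construction, because anyone recruited must have consented. The documents do not support that. On the approached reading the ratio is the consent rate, and naming two separate counts suggests that the authors saw them as different. Even on the enrolled reading, the order of consent (Section 11.4) and eligibility screening (Section 6.1) is not fixed. If consent comes first, screen failures lower the ratio.

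A reader might also infer that the study cannot produce a recruitment estimate. That is too strong as well. Monthly accrual can be worked out from enrolment dates, and the Recruitment Log may hold the missing counts. The log data mentioned in Section 7 are introduced by a non-exhaustive example, so use of that log is not excluded, although the example points to treatment sessions.

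The best defence is Section 13: slow recruitment would fail the protocol's own key benchmark, and Sections 8.5.1 and 10.1 have the team discuss recruitment monthly. It can be added that exact intervals at every recruitment stage are good practice in a descriptive pilot of 25, and that their absence is not an error.

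These objections narrow the point but do not remove it. Section 13 is not connected to the Section 7 verdict, so a study could miss the benchmark and still be reported as feasible. A primary-aim statistic that could be read as 100% or about 30% in the same study still needs a definition.

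**Conclusion.** The point holds in this form: the participation rate is undefined, no screened or eligible denominator is stated on either reading, and the Section 7 verdict omits recruitment although it is the first primary-aim component.

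The firmest part is the verdict rule. It would accept accrual of about 1.2 per month against a stated minimum of 6, assuming that 25 are enrolled and that the 24 months contain no start-up or analysis time. Allowing for such time would raise the slowest feasible pace but would not bring accrual into the rule.

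The effect on the uptake figure cannot be sized from the documents. A reader might infer that planning of the larger trial would be wrong by some fixed factor, but any such factor only restates an assumed approached count. With 28 approached, the gap between 100% and 89% is small. With 84 it is large. If recruited means approached, there is no error in that figure. Nor do the documents show that the log already holds the needed counts, because its content is not described. The change should be made while recruitment can still be logged prospectively, since refusals may be impossible to reconstruct afterwards.

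**What to change.** 1. In Section 7, replace the undefined phrase with consented/approached as the participation rate, with an exact 95% CI. Define approached so that it includes patients who decline before expressing interest, and state whether eligibility is checked before or after consent.
2. Report the numbers screened, eligible, approached, consented and treated, with reasons for ineligibility and refusal. This also supplies the missing analysis of barriers to recruitment.
3. In Section 6.1, list these items as required Recruitment Log fields.
4. Report accrual by month against the minimum of 6 per month in Section 3.1.1, and make it part of the feasibility verdict in Section 7, so that the verdict agrees with Section 13. Add recruitment to the feasibility outcomes listed in Section 3.1.

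The cost is a few log fields, some staff time to complete them for patients who do not enrol, and one more table. The sponsor also accepts a verdict that is harder to meet, and a participation rate that may look less favourable than one starting at consent.

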12.3 Subject Payments

All participants will be provided with a financial token of appreciation that increases slightly the longer they are in the study (\$15 for baseline, \$20 for end of intervention, \$20 for 4-week post-intervention, and \$25 for 8-week post-intervention).

13 Benchmarks for Study/Publication Plan

The key benchmark for success of this study is to complete recruitment goals and data collection as scheduled. The information gathered from this study will provide important data for designing a large clinical trial that tests the efficacy of LLLT on lymphedema in the HNC survivors. Additional benchmarks for success include: 1) dissemination of preliminary findings at professional conferences and 2) submission of articles to peer-reviewed journals.

CONFIDENTIAL

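### Section 7 can declare feasibility without any look at accrual over time, although recruitment is the first-listed part of the primary endpoint and a minimum of 6 per month is stated

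*Combined protocol and SAP*

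**What the plan says.** Recruitment is prominent in the aims. The Study Summary opens the primary aim with "specifically to 1) obtain recruitment estimates and determine barriers to recruitment". Section 3.2.1 says "The primary endpoint will be the feasibility of LLLT in HNC patients, including recruitment estimates, barriers to recruitment, and barriers to implementation", followed by safety and satisfaction. Section 3.1.1 gives the only target over time: "We will recruit a minimum of 6 participants per month". Section 13 adds "The key benchmark for success of this study is to complete recruitment goals and data collection as scheduled".

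Section 7, in the paragraph on the primary aim, bases its conclusion on two other quantities: at least 80% of participants completing the study activities, and at least 80% who "will report acceptable levels of satisfaction with the interventions, thereby demonstrating feasibility of the interventions proposed in this research". Its descriptive summaries include a participation ratio (recruited against consented), with no threshold and no unit of time. Nothing listed there compares achieved accrual with 6 per month.

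The documents are not uniform about what feasibility covers. Section 3.1 describes feasibility of the intervention as barriers to implementation, safety and satisfaction, and leaves recruitment out.

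**The concern.** Completion and satisfaction are both proportions of those who entered. Neither can register how long it took to find them, and nor can the recruited-to-consented ratio: every person approached could consent while very few are approached each month. A trial that follows section 7 exactly could therefore report feasibility as demonstrated when accrual ran far below the stated minimum.

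This matters because section 13 says the pilot is to supply data for designing a large trial. Accrual per month at a centre of this kind drives the number of sites and the length of that trial. If the headline is simply that feasibility was demonstrated, a reader may take recruitment to be covered, since 3.2.1 lists it under the same word.

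**Working it through.** **Inputs**
- Target rate: 6 per month (3.1.1).
- Sample size: "Total number of subjects: 25" (4.5).
- Time per participant: "The duration of the study subjects' participation will be 10 weeks" (4.4), that is 10 × 12 / 52.18 = 2.30 months.
- Study duration: 24 months (Study Summary).
- Section 7 thresholds: 0.80 × 25 = 20 completing and 20 satisfied.
- Assumptions: the target in 3.1.1 counts people enrolled; enrolment is steady. The documents give no accrual period and no derivation of the 6 per month, so there is no accrual calculation of the plan's own to reproduce.

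**Step 1: the timetable implied by the target.** 25 / 6 = 4.17 months to enrol; 4.17 + 2.30 = 6.47 months to the last visit. The 24-month duration leaves 24 − 6.47 = 17.53 months of slack, so it does not enforce the target.

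**Step 2: how slow accrual can be while still giving 25 participants.** Rate = 25 / (months open); ratio = rate / 6.

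| Assumed months open | Rate per month | Share of 6 |
|---|---|---|
| 24 (whole study) | 25 / 24 = 1.04 | 17% |
| 24 − 2.30 = 21.70 | 25 / 21.70 = 1.15 | 19% |
| 21.70 − 3 = 18.70 | 25 / 18.70 = 1.34 | 22% |
| 21.70 − 6 = 15.70 | 25 / 15.70 = 1.59 | 27% |

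The last two rows allow for 3 or 6 months lost to start-up or analysis. In every row, 20 of 25 completing and 20 of 25 satisfied meets section 7.

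**Step 3: the rule itself has no floor.** Its criteria are percentages, so 8 of 10 also reaches 80%. Ten enrolled over 21.70 months is 0.46 per month, 8% of the target.

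**Step 4: can 25 participants tell slow accrual from planned accrual?** Enrolment stops at a fixed 25 and the time T is random. For steady Poisson accrual the exact 95% limits use chi-square with 2 × 25 = 50 degrees of freedom at both ends: lower 32.36 / (2T) = 16.18 / T, upper 71.42 / (2T) = 35.71 / T.
- T = 21.70 months: 0.75 to 1.65 per month.
- T = 4.17 months: 3.9 to 8.6 per month.

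The intervals do not overlap, so the comparison is informative even at this size.

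**Step 5: how a criterion would behave.**
- Interval wholly below 6: needs 35.71 / T < 6, so T > 5.95 months, an observed rate below 25 / 5.95 = 4.20 per month. A site truly recruiting at 6 would be judged short 2.5% of the time.
- Observed rate at least 6: a site truly recruiting at 6 would miss this 47% of the time (Poisson with mean 25, at most 24 enrolments in 4.17 months).
- Lower limit at least 6: needs T ≤ 16.18 / 6 = 2.70 months, about 9.3 per month observed.

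**The case against.** The strongest reply is that section 7 and section 13 judge different things. Section 7 speaks of feasibility of the intervention, and 3.1 describes that without recruitment; section 13 speaks of success of the study. A treatment can be workable and well liked while the study recruits slowly. A reader might infer that the two sections contradict each other outright. The documents do not support that: the conflict is partial, because 3.1 leaves recruitment out while the Study Summary and 3.2.1 put it in. What survives is that section 7 presents its rule as the analysis of the primary aim, and the primary endpoint includes recruitment.

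Second, the recruitment aim is to estimate. A reader might infer that slow accrual means the first part of the primary aim has failed. That goes too far: a slow rate, once reported, is still an estimate obtained, and safety and barriers also have no threshold. But section 7 does not commit to reporting a rate over time at all.

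Third, slow accrual would not go unseen. A recruitment log is kept (6.1), the team reviews recruitment monthly (8.5.1, 10.1), and the section 13 benchmark would be missed. This is fair, but none of these commits the report to a rate, a comparison with 6 per month, or a limit on the feasibility statement.

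Fourth, section 7 words its percentages as expectations. It nevertheless says that meeting them demonstrates feasibility, and no other rule is given.

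Finally, making 6 per month a hard pass mark would be poor practice, since no basis for the figure is given and step 5 shows how often a site on target would miss it. That objection stands, and the fix respects it.

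**Conclusion.** The point holds. As written, section 7 supports a statement about completion and satisfaction among those enrolled, not about feasibility as 3.2.1 defines it, because accrual over time enters neither the rule nor the listed summaries. With 25 enrolled over most of the study, accrual of about 1.0 to 1.6 per month (17% to 27% of the stated minimum) would still be reported as feasible.

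That range is an illustration. It assumes enrolment open for roughly 16 to 24 months, steady entry, and that the 3.1.1 target means enrolled. A reader might take about one fifth as the lowest rate the rule allows; it is only the case of 25 enrolled over 21.70 months, and step 3 shows that the rule has no lower limit. The absence of an accrual element depends on none of these assumptions. Completion, satisfaction and safety results are unaffected; what changes is how far the primary conclusion may reach.

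**What to change.** 1. In 3.1.1, state that the target counts participants enrolled.
2. In section 7, add the number enrolled per open month, with an exact 95% interval suited to stopping at 25 (chi-square with 50 degrees of freedom for both limits), set beside the 6 per month. Leave any halt under 8.4 out of the open months, so that a safety pause is not counted as slow recruitment. If enrolment closes on a date before 25 is reached, use the fixed-time exact Poisson interval instead.
3. State that meeting both 80% criteria supports feasibility and acceptability of the intervention among those enrolled only.
4. State that if the accrual interval lies wholly below 6 per month, the report will conclude that recruitment was not feasible at the planned rate. Do not make an observed rate of at least 6 a condition for feasibility.
5. Reconcile 3.1 with the Study Summary and 3.2.1 on whether feasibility includes recruitment, and have section 13 refer to the same accrual figure.

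The cost is protocol wording and one rate from enrolment dates and site-open dates; no study procedure changes. The downside is that the overall feasibility claim becomes narrower.
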